**EXPERIMENTAL DESIGN AND METHODS:** *Participants.* We will recruit 60 largely sedentary (< 1 hour/week of purposeful aerobic exercise for the past 6 months), though otherwise medically healthy, participants with MCI or cognitive complaints, ages 55-80. Participants will be randomized to the walking intervention (n=20), a CT program (n=20), or a combined walking and CT intervention (n=20). Participants will be recruited from the Memory and Aging Resilience Center (MARC), the Alzheimer's Disease Research Center (ADRC) and multiple existing studies of aging at the University of California, San Diego (UCSD) who consented to be contacted about other studies. We will over-recruit by 10% to account for subject attrition and to ensure a final sample size of 60. These sources should allow for realistic attainment of the desired sample size and recruiting from these extant sources is optimal given that many have already been screened for general health and gross cognitive status. Should these recruitment avenues be insufficient, however, additional community participants will be recruited. All participants will be screened and excluded if they have a history of significant head trauma, other neurologic or major psychiatric disorders, known dementia, current substance dependence, or any contraindication to increased physical activity. Participants must also be fluent in English, willing to commit to the time requirements of their assigned intervention, and be free of sensory or mobility deficits that would interfere with the interventions. Participants not showing sufficient adherence to their intervention protocol will be discontinued from the study. If not administered by the recruitment source in the last 6-weeks, the Montreal Cognitive Assessment (MoCA) and the Clinical Dementia Rating Scale (CDR) will be included in the screening; MoCA must be 18-30 and CDR of 0 or 0.5 at entry into the study. Participants cannot be engaged in another cognitive training or exercise trial during participation during this investigation. Individuals over age 80 will not be included due to increased risk of mobility difficulties and safety concerns in the oldest-old with the walking protocol.

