memory, 'Syllable Stacks,' a working memory module, 'Divided Attention,' 'Mixed Signals,' targeting inhibition, 'In the Know,' for story learning, and 'Face Facts,' for name learning. Participants will use the program 60 minutes/day, 5 days/week for 12 weeks. They will receive a brief introduction to the program on site at the MARC (log-in, which modules to complete, and how long to spend each day on CT). These instructions will then be repeated via phone once the participant is on their home computer and can be supplemented by an in-home visit if significant technological difficulties exist. If participants do not have a home computer/internet access, they can complete the modules at another location such as a public library, senior center, or at the MARC, but training will still be self-directed. Brain HQ offers a secure clinician portal that allows for monitoring of usage and progress of participants but the study coordinator will still be in weekly phone contact with participants to discuss activity logs and answer any questions.

The combined condition will concurrently follow both the walking and the CT programs as described above.

*STATISTICAL ANALYSES:* Assuming a one tailed test, a medium effect size with power of .7 can be obtained with the sample size of 20 per group. The groups will be compared on baseline characteristics, including program adherence, using t-tests and  $\chi^2$  and analyses will be adjusted to account for any observed group differences. Lifestyle covariates such as health, prior physical activity, mood, and education will also be explored and used as appropriate. We will employ reliable change analyses to take into account change in neuropsychological test scores over the course of the intervention while also accounting for predicted practice effects. To address the primary hypothesis, group comparisons of changes in neuropsychological test scores and measures of daily functioning between the groups will be determined via ANCOVA and repeated measures analyses. For the CT condition in particular, we will examine whether any cognitive benefits generalize beyond the trained task. To address the secondary hypothesis, we will use logistic regression to determine the degree to which intervention group predicts differential cognitive outcomes. Correlations between neuropsychological test scores and health and fitness variables will also be explored.

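### Covariates are picked by testing the arms for differences, adherence included, and by exploration, so no prognostic covariate is guaranteed and a post-randomisation variable can enter the model

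*Combined protocol and SAP*

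**What the plan says.** All of this is in the Statistical Analyses section of the combined protocol and SAP.

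- **Rule 1, test then adjust.** The arms are compared on baseline characteristics by t-tests and chi-square, with program adherence counted among those characteristics. Then "analyses will be adjusted to account for any observed group differences". No significance threshold and no list of variables is given.
- **Rule 2, exploration.** "Lifestyle covariates such as health, prior physical activity, mood, and education will also be explored and used as appropriate". The list is open, and nothing says what makes a covariate appropriate.
- **Model.** Group comparisons of change in test scores and daily functioning "will be determined via ANCOVA and repeated measures analyses". No covariate of the ANCOVA is named.

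The Participants paragraph establishes that allocation is random: "Participants will be randomized to the walking intervention (n=20), a CT program (n=20), or a combined walking and CT intervention (n=20"). No other part of the document fixes a covariate set.

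**The concern.** A between-arm test on a baseline variable asks whether the arms differ. Under randomisation they differ only by chance, so the answer says nothing about whether the variable predicts outcome, which is the only reason to adjust for it. A flagged variable is also, by construction, correlated with arm in this sample, and that correlation inflates the variance of the arm contrast. Meanwhile the variable most likely to help, the outcome's own baseline score, is collected but not explicitly placed in the model.

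Adherence is a different and sharper problem. It does not exist at baseline. It is produced during the 12-week programs, and it may well differ by arm because the combined arm has to follow both programs. A difference in adherence is then not a chance imbalance but a possible consequence of assignment, and conditioning on it can bias the comparison the trial was randomised to make.

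Finally, an open covariate list leaves the reported results dependent on choices made once the data are in hand. The affected comparisons are combined versus walking and combined versus CT, on many outcomes, at two post-intervention visits.

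**Working it through.** **Inputs.** From the documents: three arms of 20, a one-tailed test, a medium effect and power 0.7. Not stated, so assumed: alpha 0.05 one-sided; medium means d = 0.5 in raw-score SD; baseline-outcome correlation rho 0.5 to 0.7; 5, 8 or 20 independent tested variables; one prognostic covariate with partial correlation 0.3.

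**1. The plan's own figure.** "Assuming a one tailed test", the plan says "power of .7 can be obtained with the sample size of 20 per group". For 20 versus 20, approximate power is Φ(d·√(n/2)/√(1−rho²) − 1.645).
- Unadjusted: 0.5 × √10 = 1.581; 1.581 − 1.645 = −0.064; power 0.475 (0.463 by noncentral t).
- Baseline score as covariate, rho 0.7: 1.581/0.714 = 2.214; 2.214 − 1.645 = 0.569; power 0.715.

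The stated 0.70 does not follow from an unadjusted comparison of two arms at d = 0.5. Baseline-adjusted ANCOVA comes close only with rho near 0.7. Whether 0.70 is justified is a separate question, but it shows how much the covariate choice matters here.

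**2. How often the rule fires.** With three pairwise t-tests at two-sided 5%, simulation gives a flag rate of about 12.5% per variable. The chance of at least one flag is 1 − 0.875^k: 49% for k = 5, 66% for k = 8, 93% for k = 20. The expected number flagged is 0.125k: 0.6, 1.0 and 2.5. Correlated variables would make at least one flag less likely.

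**3. Why a flag costs precision.** In a two-arm comparison, a covariate just significant at 38 degrees of freedom has t ≈ 2.024. Its squared correlation with arm is 2.024²/(2.024² + 38) = 4.10/42.10 = 0.097. If it does not predict outcome, adding it multiplies the variance of the arm contrast by 1/(1 − 0.097) = 1.11.

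**4. Power, baseline score in the model** (3 × 20, 8,000 replicates; % at rho 0.5/0.6/0.7). The fixed model is baseline score plus the prognostic covariate: 58/65/72.

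| Variables tested | Baseline + flagged | Baseline alone | Loss vs baseline alone | Loss vs fixed model |
|---|---|---|---|---|
| 5 | 54/60/69 | 55/61/70 | under 1 before rounding | 4/5/3 |
| 8 | 55/60/67 | 56/62/69 | 1/2/2 | 3/5/5 |
| 20 | 51/58/65 | 56/63/69 | 5/5/4 | 7/7/7 |

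Across repeated simulations the losses against baseline alone were about 0.5, 1 to 3 and 4 to 5 points, and against the fixed model about 3 to 8.

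**5. Power if the baseline score is left out.** Change score plus flagged variables (20 tested) gives 42/51/60. Against 51/58/65 with the baseline score in, the further loss is 9/7/5 points.

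**6. Type I error.** A separate simulation of one pairwise comparison with 8 candidate covariates gave 4.4 to 5.2% under imbalance testing, and 5.0 to 5.4% with the baseline score plus prespecified prognostic covariates. Reporting the most favourable of the 2⁴ = 16 subsets of four covariates gives 7.3/9.6/12.8/17.8% when each correlates 0.1/0.2/0.3/0.4 with outcome.

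**7. Adherence.** No arithmetic applies. The Statistical Analyses section calls it a baseline characteristic, whereas the intervention descriptions have it arising from activity logs and program usage after assignment. Rule 1 would put it in the model if the arms differed on it.

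**The case against.** Several points on the other side stand.

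- **ANCOVA may already mean baseline-adjusted**, and a repeated-measures model includes the baseline visit. A reader might attribute to the selection rule the whole gap between change scores with flagged variables (42/51/60%) and the fixed model (58/65/72%), which is 16/14/12 points. That is not supported. Change scores with no covariates give 46/55/64%, so the rule accounts for about 4 points of the gap even with 20 variables tested; most of the rest is the omitted baseline score.
- **The plan does name plausibly prognostic variables**: health, prior activity, mood and education. A reader might infer that it adjusts for chance imbalances in place of prognostic variables. The text supports only that none is guaranteed entry.
- **The number of tested variables is undocumented.** Near-certain flagging needs something like 20 variables; with 5 it is about an even chance, and the loss is then negligible against baseline score alone.
- **A reader might infer that the rule inflates the false-positive rate.** Imbalance testing alone does not. The 7 to 18% needs the covariate set to be picked for a favourable result. The open wording permits that but states no such intention.
- **Adjusting for an imbalance in a truly prognostic variable is sensible.** Granted, but naming it in advance secures that benefit whichever way the arms fall.

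None of this supplies a fixed covariate list, and none of it answers the point about adherence.

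**Conclusion.** The concern holds in this form. The plan states a selection rule that does not identify prognostic covariates, guarantees none of them a place, and makes a post-randomisation variable eligible for adjustment.

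The power cost of the rule itself is small to moderate: negligible with few tested variables, 4 to 5 points with 20 against baseline score alone, and about 3 to 8 points against a fixed model with one good covariate. Another 5 to 9 points go if the baseline score is not in the model. These sizes rest on the assumed effect, alpha, correlations and variable counts, none of which the documents give; the direction does not depend on their exact values. Type I inflation is a worst case that the wording allows, not a property of imbalance testing. There is also no single primary p-value to inflate: the flexibility is spread over many outcomes, two visits and two contrasts.

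The bias from adjusting for adherence cannot be sized from the documents, but it concerns validity and not just precision.

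**What to change.** In the Statistical Analyses section:

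1. Delete the test-then-adjust rule and the sentence on exploring lifestyle covariates.
2. For each outcome and visit, specify ANCOVA of the post-intervention score on arm, with that outcome's own baseline score plus a short list of covariates measured before randomisation (for example age and education), fixed before outcome data are seen.
3. Keep program adherence out of the primary model. Report it descriptively by arm as a post-randomisation variable.
4. Present baseline characteristics by arm without significance tests.
5. Report models with any other covariate only as labelled sensitivity analyses.

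The cost is a few sentences and no new data. The downside is one or two degrees of freedom for the fixed covariates.

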Study Protocol and Statistical Analysis Plan

Document Date: May 4, 2018

ID: NPSASA-14-321959      Impact of Combined Behavioral Interventions on Cognitive  
NCT: 02864069                      Outcomes in MCI

**SPECIFIC AIMS/HYPOTHESES:** Primary Aim: Compare the efficacy of participating in singular [(walking *or* computer training (CT)] vs. combined (walking *and* CT) behavioral interventions in maintaining/ improving cognitive functioning, quality of life (QOL), and daily functioning, in 60 adults with mild cognitive impairment (MCI) or cognitive complaints, ages 55-80. Primary hypotheses: 1: The combined group will show greater cognitive benefits (objective neuropsychological and ecological measures of cognition) 0- and 3-months post-intervention than either singular intervention group. 2: The combined group will have greater QOL benefits (patient and informant self-report) and maintenance of independent functioning (Independent Living Scales; ILS, CDR) 0- and 3-months post-intervention than either singular intervention group. Secondary Aim: Compare any differential cognitive benefits of physical vs. cognitive interventions. Secondary hypothesis: Walking will result in greatest benefits to executive functioning while CT will result in greatest benefits to memory.

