not previously given. All participants will obtain medical clearance by a physician to participate in the protocol and provide basic medical information (including medical history, basic health and fitness variables, stroke risk factors, blood pressure, height, weight, and body mass index). All participants will undergo neuropsychological assessment on three occasions: a baseline assessment, immediately post-intervention (0-month post), and extended follow-up at 3-months post-intervention (3-month post). Based on prior research, the assessment measures were chosen to cover executive functioning and memory, daily functioning, and informant report of functioning, in particular. Ecological measures of cognition are also included to be able to determine generalizability and impact on everyday functional skills. The baseline assessment will entail a comprehensive neuropsychological exam consisting of measures of global cognitive functioning and estimated premorbid intellectual functioning (American National Adult Reading Test; ANART) the Wechsler Abbreviated Scale of Intelligence (WASI), language (the Boston Naming Test (BNT), memory (Hopkins Verbal Learning Test (HVLT), executive functioning [selected subtests from the Delis Kaplan Executive Functioning System (DKEFS)], attention/working memory from WAIS-IV: Symbol Search, and Digit Span, Symbol-Digit Modalities Test (SDMT), the CDR, and an ecologically valid assessment of cognitive functioning (Rivermead Behavioural Memory Test; RBMT) that will test some skills specifically trained in the CT condition (e.g., name learning, and story learning) but also additional untrained skills such as prospective memory. We will also administer the ILS, a practical measures of functional living skills (Loeb, 1996), the Everyday Cognition Scale (ECog), an informant-based questionnaire of everyday cognitive skills with multiple scales covering memory, language, visuospatial abilities, executive functioning, and divided attention (Farias et al., 2008), a self-report measure of mood (the Geriatric Depression Scale), a measure of QOL, the Quality of Life Interview-Brief Version [QOLI-Brief (Lehman, Kernan, & Postrado, 1994)], and a self-report assessment of current and past physical activity including the Community Health Activities Monitoring Program for Seniors (Stewart et al., 2001).

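### The secondary hypothesis is assigned to logistic regression with no categorical outcome defined, although both domains are scored tests and the linear models already planned would have more power

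*Combined protocol and SAP*

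**What the plan says.** The hypothesis is in SPECIFIC AIMS/HYPOTHESES: "Walking will result in greatest benefits to executive functioning while CT will result in greatest benefits to memory". Its analysis is a single sentence in STATISTICAL ANALYSES: "To address the secondary hypothesis, we will use logistic regression to determine the degree to which intervention group predicts differential cognitive outcomes".

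Four other statements bear on it.

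- **Measures** (EXPERIMENTAL DESIGN AND METHODS, Procedures): "memory (Hopkins Verbal Learning Test (HVLT), executive functioning [selected subtests from the Delis Kaplan Executive Functioning System (DKEFS". Both are scored instruments. The DKEFS subtests are not named.
- **Visits** (same section), after baseline: "immediately post-intervention (0-month post), and extended follow-up at 3-months post-intervention (3-month post". The primary hypotheses name both visits; the secondary hypothesis names neither.
- **Reliable change** (STATISTICAL ANALYSES): "We will employ reliable change analyses to take into account change in neuropsychological test scores over the course of the intervention", with allowance for practice effects. No category or threshold is given, and there is no link to the logistic model.
- **Linear models** (STATISTICAL ANALYSES), introduced as addressing the primary hypothesis: "changes in neuropsychological test scores and measures of daily functioning between the groups will be determined via ANCOVA and repeated measures analyses".

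**The concern.** With intervention group as the predictor, a logistic model needs a categorical outcome, and the plan defines none. The threshold, the visit, the DKEFS subtests and the form of the executive-versus-memory comparison could therefore all be settled after the data are seen.

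There is also a cost in efficiency. The tests yield scores, and turning a score into categories discards information. With 20 per arm there is little to spare. The same paragraph already contains models that keep the scores intact, and it gives no reason for leaving them for this hypothesis.

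**Working it through.** **Inputs.** From the documents: one-tailed testing, a medium effect and 20 per arm. Assumed, because the documents do not give them: alpha .05, d = 0.5 for a medium effect, a normal mean shift, and all cut-offs and correlations.

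**1. The plan's own figure.** The plan states: "Assuming a one tailed test, a medium effect size with power of .7 can be obtained with the sample size of 20 per group". For two groups of 20 the noncentrality is 0.5 × √(20/2) = 1.58. With 38 degrees of freedom and one-sided alpha .05, the noncentral t gives power .463, not .70. About .70 is reached by ANCOVA with a baseline correlation near .70, or by a one-sample or paired test with n = 20 (.695). Alpha, test and correlation are unstated, so this check does not show the figure to be wrong, and the point here does not depend on it.

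**2. One domain, binary cut.** Let p be the responder proportion in the reference arm. The cut is c = Φ⁻¹(1 − p), and the other arm's proportion is 1 − Φ(c − 0.5). Power of the one-sided score test comes from enumerating all 21 × 21 tables:

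| Reference responders | Other arm | Expected responders among 40 | Power |
|---|---|---|---|
| 50% | 69.1% | 23.8 | .323 |
| 40% | 59.7% | 19.9 | .317 |
| 30% | 49.0% | 15.8 | .324 |
| 20% | 36.6% | 11.3 | .325 |
| 10% | 21.7% | 6.3 | .269 |
| 5% | 12.6% | 3.5 | .208 |

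Against .463, the loss is about 14 points at 20 to 50% responders, 19 at 10% and 25 at 5%. The actual size of the test at 5% is only .028, so part of that last loss is discreteness.

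**3. One domain, three ordered categories.** This was simulated with the rank-type score test that corresponds to an ordinal logistic model. Splits of 20/60/20 or thirds give 39 to 40%, and 10/80/10 gives 34%. The loss is 46 − 40 = 6 to 46 − 34 = 12 points.

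**4. Baseline-adjusted.** The effective shift is 0.5/√(1 − r²), which is 0.577 at r = .5 and 0.700 at r = .7. ANCOVA (simulated, slope estimated) has power .551 and .693. A binary cut on the baseline-adjusted change with 20 to 50% responders has about .40 and .51 to .52. The loss is about 15 points at r = .5 and 18 at r = .7.

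**5. Comparing the two domains.** Let c now be the correlation between the domain scores. The executive-minus-memory difference has SD √(2(1 − c)). If each arm leads by 0.5 SD in its own domain, the group-by-domain effect is 1/√(2(1 − c)); if only one domain differs, it is 0.5/√(2(1 − c)). Power on the scores:

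| Rule and scenario | c = 0 | c = .3 | c = .5 |
|---|---|---|---|
| Group-by-domain, both domains differ | .709 | .836 | .928 |
| Group-by-domain, one domain differs | .292 | .370 | .463 |
| Both one-domain tests required, both differ | .214 | .169 | .137 |

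If walking leads by 0.5 SD in both domains, the group-by-domain test rejects only 5% of the time.

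**The case against.** The strongest reply is that the plan never says scores will be dichotomised. Logistic models also cover ordered categories, and reliable improvement, no change and decline would be a natural reading of the reliable change analyses. This stands. A reader might infer a fixed loss of 14 to 19 points, but that applies to binary outcomes only. The three-category cases in step 3 lose as little as 6. Because the outcome is undefined, only a range can be given.

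Second, a reader might blame the logistic model for an uninformative null result. The documents do not support that. At 20 per arm and d = 0.5, the unadjusted test on the score itself has only 46% power. Categorising worsens a shortage that sample size already creates.

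Third, the planned ANCOVA and repeated measures can yield a walking-versus-computer-training contrast, and the hypothesis does name the domains and the direction. This also stands, so it would be too strong to say that the plan has no means of comparing the two arms on scores. But those models are assigned to the primary hypothesis, and nothing makes their contrast the test of the secondary one.

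Fourth, one might conclude that a group-by-domain contrast should decide. That is a choice of estimand. A positive result shows a differential benefit but establishes neither half of the hypothesis, and its power is 29 to 37% at a between-domain correlation of 0 to .3 if only one domain differs.

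**Conclusion.** The point holds in a limited form. That the outcome, threshold, visit and domain comparison are undefined is plain from the text and rests on no assumption. The loss of power is conditional on a roughly normal mean shift and the same contrast. With 20 per arm, one-sided alpha .05 and d = 0.5, it is about 6 to 25 percentage points for one domain, across the outcome definitions tried. With baseline adjustment, ANCOVA has 55% or 69% power (baseline correlation .5 or .7), against about 40% or 51% for a binary cut.

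The documents do not support reading this as a commitment to dichotomise, or as the sole cause of low power. The primary hypotheses are untouched. The sponsor should make the change because a better method is already in the plan.

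**What to change.** Make the main secondary analysis a baseline-adjusted linear model (ANCOVA or repeated measures) of walking versus computer training, on pre-specified executive and memory scores at one named visit. Keep a reliable-change analysis by logistic regression as supportive, with its categories and threshold defined beforehand.

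State in advance whether the decision rests on the two one-domain contrasts or on a group-by-domain contrast. That choice belongs to the sponsor: the first addresses each half of the hypothesis but has low power if both tests must succeed, and the second has the limits given above.

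If logistic regression stays as the main analysis, the minimum repair is to define its outcome, threshold, visit and domain comparison before analysis.

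The cost is small: no new data and no new model family. The downside is that the tests and weights in each domain score (including which DKEFS subtests), the visit and the decision rule must all be fixed before analysis.
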